6.4 Withdrawal of individual subjects

Subjects can leave the study at any time for any reason if they wish to do so without any consequences. The investigator can decide to withdraw a subject from the study for urgent medical reasons.

6.5 Replacement of individual subjects after withdrawal

Patients that meet inclusion criteria will be invited for participation in the study. When patient agrees to participate in the study, informed consent is signed. When patient decides to withdraw after start of the treatment period, new patients can be admitted to the study to reach the required sample size.

6.6 Follow-up of subjects withdrawn from treatment

Subjects who withdraw from the study will be followed up according to the routine terms of patient care at the outpatient clinic or revered back to their general practitioner.

6.7 Premature termination of the study

There are no predefined criteria for premature termination of the study. If, however, during the conductance of the study information becomes available showing that continuation of the study would result in a significant safety risk for the patients, the principal investigator and project leader will decide to terminate the study.

7. SAFETY REPORTING

7.1 Section 10 WMO event

In accordance to section 10, subsection 1, of the WMO, the investigator will inform the subjects and the reviewing accredited medical ethics committee if anything occurs, on the basis of which it appears that the disadvantages of participation may be significantly greater than was foreseen in the research proposal. The study will be suspended pending further review by the accredited medical ethics committee, except insofar as suspension would jeopardize the subjects' health. The investigator will take care that all subjects are kept informed.

7.2 AEs, SAEs and SUSARs

7.2.1 Adverse events (AEs)

An adverse event is any untoward medical occurrence in a patient administered a medicinal product and which does not necessarily have to have a causal relationship with this treatment. An adverse event can therefore be any unfavourable and unintended sign (for example, an abnormal laboratory finding), symptom, or disease temporally associated with the use of a medicinal product, whether or not considered related to this medicinal product. (ICH E2D)

7.2.2 Serious adverse events (SAEs)

A serious adverse event is any untoward medical occurrence or effect that at any dose:

- results in death;
- is life threatening (defined as an event in which the subject was at risk of death at the time of the event; it does not refer to an event which hypothetically might have caused death if it were more severe);
- requires hospitalisation or prolongation of existing inpatients' hospitalisation;
- results in persistent or significant disability or incapacity;
- is a congenital anomaly or birth defect;
- is an important medical event (defined as a medical event [s] that may not be immediately life-threatening or result in death or hospitalization but, based upon appropriate medical and scientific judgment, may jeopardize the subject or may require intervention [eg, medical, surgical] to prevent one of the other serious outcomes listed in the definition above.) Examples of such events include, but are not limited to, intensive treatment in an emergency room or at home for allergic bronchospasm; blood dyscrasias or convulsions that do not result in hospitalization.)

AEs will be recorded in the eCRF as:

- AEs
- An SAE
- If the AE is the reason for permanent discontinuation from investigational product (DAE), if the AE leading to Investigational Product interruption or dose reduction
- An AE of interest
 - Urinary Tract Infection or Genital Infections
 - Potential DKAs
 - Volume depletion
 - Fractures
 - Major hypoglycaemic events
 - Acute kidney injury
 - Amputation or related events

7.2.3 Adverse events of interest

Urinary tract infection or genital infections

All potential events of urinary tract infection or genital infections will be recorded in the eCRF.

Diabetic ketoacidosis (DKA)

All potential events of DKA will be recorded in the eCRF.

Volume depletion

Events of volume depletion (eg, dehydration, hypovolemia, or hypotension) will be collected on the eCRF as AEs.

Fractures

All fractures will be recorded in the eCRF as AEs and on a separate eCRF page.

Major hypoglycaemic event

A major hypoglycaemic event is defined as an event that requires assistance of another person to actively administer carbohydrates, glucagon, or take other corrective actions. Plasma glucose concentrations may not be available during an event, but neurological recovery following the corrective actions is considered sufficient evidence that the event was induced by a low plasma glucose concentration. Major hypoglycaemic episodes will be recorded in the eCRF as an AE and on an additional eCRF page.

Acute Kidney Injury

Acute kidney injury is defined as an increase of 40% in serum creatinine from the previous visit or hospitalization due to acute kidney injury. All acute kidney injury events will be recorded on a separate eCRF.

Amputation and related events:

Amputations and related events will be recorded in the eCRF. Information on the actual amputations will be captured on a specific eCRF page.

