To reduce intraglomerular hypertension, current guidelines recommend the use of RAAS blockers as the gold standard therapy for individuals with diabetic nephropathy or in patients with heart failure ²⁶. However, despite the use of these agents, renal function continues to decline – a scenario that can be worsened in the presence of combined cardiac and renal disease. Therefore, there is a need to widen the therapeutic armamentarium for individuals with diabetes and cardiorenal disease nephropathy. SGLT2i lowers the threshold of proximal glucose reabsorption resulting in glycosuria, and increases distal tubular sodium delivery to macula densa cells. Macula densa cells are specialized epithelial cells located at the distal convoluted tubule that sense sodium delivery and mediate afferent arteriolar vasoconstriction in response to an increase in tubular sodium. SGLT2 inhibition increases the delivery of glucose and sodium in the distal tubule and to the juxtaglomerular apparatus, which is sensed as an increase in glomerular perfusion. This leads to a tubuloglomerular feedback signal causing afferent arteriolar vasoconstriction, and an acute fall in intraglomerular pressure. These effects are clinically manifested as acute reductions in GFR and hence albuminuria, followed by renal function preservation in the longer term – as recently reported in EMPA-REG OUTCOME and the CANVAS Program. Furthermore, natriuresis diminishes extracellular plasma volume and blood pressure. Thus, SGLT2i specifically alters renal hemodynamic function by reducing intraglomerular pressure, which could be expected to translate into improved long-term kidney outcomes.

In light of the results of EMPA-REG OUTCOME and CANVAS Program, we aim to elucidate the mechanisms whereby the SGLT2i "ertugliflozin" modifies cardiorenal interactions that regulate fluid volume and neurohormonal activation in patients with T2D and HF (T2D-HF). We will test the hypothesis that ertugliflozin increases proximal tubular natriuresis, thereby reducing plasma volume, without inducing significant renal vasoconstriction or activation of the sympathetic nervous system (SNS)⁷ (see below, Figure 1). The systematic understanding of the effects of SGLT2i in the setting of HF will enable the design of rational physiology based strategies to decrease the burden of HF, which could have major clinical and research implications internationally.

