2. STUDY DESIGN

This study will use a double blind, stratified randomization trial approach involving 36 T2D-HF patients taking standard HF therapies, who will be allocated to either ertugliflozin or placebo in a 1:1 ratio (Table 1 – inclusion and exclusion criteria). For feasibility, participants will be recruited from the >4000 HF patients followed at UHN-MSH heart failure clinics and from heart failure clinics in Groningen, the Netherlands, of whom >40% have T2D. The study will consist of a screening visit, a 4-week run-in phase for those subjects not on stable ACEi/ARB treatment, followed by a 12-week double blind treatment period.

The target population will be invited for screening. Subjects who meet all entry criteria and who are already on a stable dose (no changes in dose or type of drug) of ACEis or ARBs for at least 4 weeks proceed directly to randomization. Subjects who had their ACEi or ARB medication changed during the preceding 4 weeks of the screening visit proceed to a run-in phase during which the type and dose of these drugs are stabilized. Subjects will be randomly assigned to one of the two treatments. Subjects will have their study visit in the morning in fasted condition.

Subjects will be instructed to take the study medication once daily, in the morning, except on study days; on those days, the study drug will be taken after the patient visit.

Measurements:

- During the double blind treatment period, patients will collect a 24-hour urine collection at each visit for measurement of 24-hour protein, albumin, glucose, sodium, potassium, creatinine, and urea excretion. Twenty-four hour urine collections will be performed at: Visits 3, 4 and 8. Routine biochemistry and safety labs will be drawn at screening, during each physiological assessment and at each the specified office safety visits (see visit schedule table below).
- Office systolic and diastolic blood pressure measurements, heart rate, weight, and waist circumference will be performed at screening and at each subsequent physiological testing day and at each office visit (see visit schedule table below).
- Blood will be drawn for measurement of renal function tests, HbA1c, glucose, complete blood count, plasma albumin, RAAS biomarkers, natriuretic peptides, and neurohormones on visits 3, 4 and 8.
- Blood and urine samples will be stored for future exploratory biomarker analyses to study the effect of ertugliflozin in this study population.

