The randomization visit procedures should be completed on a single day under a euglycemic clamp. As part of the study procedures, blood glucose will therefore be maintained between 4-6 mmol/L during the long study days. From a patient perspective, the procedures involved in the trial involve three intravenous needles (for renal function assessments, infusion of insulin and dextrose and finally for blood-letting). The randomization visit procedures will include measures of natriuresis, renal and systemic hemodynamic function, neurohormonal assessments, echocardiography, arterial stiffness, plasma volume, bioimpedence spectroscopy, vital signs, weight and waist circumference, blood and urine samples collection. Cardiac output and systemic vascular resistance will also be measured using non-invasive cardiac monitoring (NICOM). This Version number: 6.0

non-invasive technique is a form of bioelectrical impedance ("bioreatance") to measure thoracic fluid content with electrocardiogram electrode stickers. Beat-to-beat changes in fluid content can be used to derive cardiac output. Then, using measured mean arterial pressure, systemic vascular resistance can be calculated. This entire measurement process takes approximately 15 minutes^{8a}. The first dose of blinded study medication should only be administered one day after all randomization visit procedures have been completed.

Visit 4, 5 and 6

One week after initiation of ertugliflozin/placebo, subjects will return to the renal physiology laboratory for the 1-week assessment (Visit 4), with repeated measures of all physiological parameters described for Visit 3. They will then continue the same treatment allocation for the rest of the trial. A safety visit (vital signs, weight, waist circumference, and physical exam and safety laboratory tests) will be conducted approximately 7-10 days later (Visit 5), and again 4-5 weeks later (Visit 6).

Additional telephone visits will be scheduled as required to follow weight and home blood pressure, in line with usual clinical care. If the patient does not tolerate medication a visit to the out-patient clinic will be scheduled. At the end of the treatment period (at visits 3, 4, and 8), the patient will take study medication *BEFORE* physiological procedures are performed.

Visit 7 and 8

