The Investigator will assess causal relationship between Investigational Product and each SAE/DAE, and answer 'yes' or 'no' to the question 'Do you consider that there is a reasonable possibility that the event may have been caused by the investigational product?'

Adverse Events Based on Signs and Symptoms

All AEs/SAEs/DAEs/AE of special interest spontaneously reported by the patient or reported in response to the open question from the study personnel: 'Have you had any health problems since the previous visit/you were last asked?', or revealed by observation will be collected and recorded in the eCRF. When collecting AEs/SAEs/DAEs/AE of special interest, the recording of diagnoses is preferred (when possible) to recording a list of signs and symptoms. However, if a diagnosis is known and there are other signs or symptoms that are not generally part of the diagnosis, the diagnosis and each sign or symptom will be recorded separately.

Adverse Events Based on Examinations and Tests

The results from protocol mandated laboratory tests and vital signs will be summarised in the clinical study report. Deterioration as compared to baseline in protocol-mandated laboratory values, or vital signs will be reported as AEs if they fulfil any of the AE criteria. If deterioration in a laboratory value/vital sign is associated with clinical signs and symptoms, the sign or symptom will be reported as an AE and the associated laboratory result/vital sign will be considered as additional information. Wherever possible the reporting Investigator uses the clinical, rather than the laboratory term (e.g., anaemia versus low haemoglobin value). In the absence of clinical signs or symptoms, clinically relevant deteriorations in non-mandated parameters should be reported as AE(s). Any new or aggravated clinically relevant abnormal medical finding at a physical examination as compared with the baseline assessment will be reported as an AE.

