- Infections and infestations: vulvovaginitis, balanitis and genital infections, urinary tract infections (Common)
- *Metabolism and nutrition disorders:* Hypoglycemia; volume depletion (uncommon)
- Gastrointestinal disorders: Constipation (uncommon)
- *Musculoskeletal*: Back pain (Common)
- *Renal and urinary disorders*: Dysuria; Polyuria (Common); Nocturia (uncommon)

Common (>1/100 to <1/10) and uncommon (>1/1000 to <1/100)

Few adverse events led to discontinuation of treatment and adverse events were balanced across study groups. The most commonly reported events leading to discontinuation in patients treated Version number: 6.0 with ertugliflozin 10 mg/day were increased blood creatinine (0.4%), urinary tract infections

(0.3%), nausea (0.2%), and rash (0.2%). It should be noted that the transient rise in serum creatinine may reflect a reduction in intra-glomerular pressure which may be associated with long-term structural renal protection.

f. Pharmacokinetic considerations

The potential for clinically significant drug-drug interactions (DDIs) resulting from ertugliflozinmediated inhibition of CYP1A2, CYP2B6, CYP2C8, CYP2C9, CYP2C19, CYP2D6, or CYP3A activity, or induction of CYP1A2 or CYP3A4, is low. Hence, clinically meaningful DDIs between ertugliflozin and other oral antidiabetic drugs that are oxidatively metabolized by CYP2C9 and CYP2C8 are not anticipated. Furthermore, clinically meaningful drug interactions with concomitant medications that are substrates of breast cancer resistance protein (BCRP), P-glycoprotein (P-gp), human organic cation transporter (hOCT)2 (e.g. metformin), human organic anion transporter (hOAT)1, hOAT3 (e.g. sitagliptin), hOATP1B1 (statins), or hOATP1B3 are not anticipated.

In vitro studies with Caco-2, MDR1-MDCK, and BCRP-MDCK cells suggest that ertugliflozin may be a substrate for P-gp and BCRP-mediated efflux. However, ertugliflozin has high aqueous solubility and moderate permeability, and, following a 25-mg oral dose of [14C]ertugliflozin, more than 50% of the dose was absorbed in humans. These data, along with the dose-proportional increases in exposure observed in humans over the dose range of 0.5 to 300 mg, indicate that neither P-gp nor BCRP is likely to be a limiting factor for oral absorption of ertugliflozin.

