- 2.1. Relationship between proximal renal tubular natriuretic effects and volume reduction: proximal renal tubular natriuretic effects will be evaluated by lithium clearance FE(Li+); volume change will be measured using the following two outcomes:
 - a. Plasma volume (PV)
 - *i.* Measured by indocyanine green (for site 2 and 3)
 - ii. Estimated percent change by Strauss estimation
 - $([{Hb_{baseline}/Hb_{end}} \times {(100-Ht_{end})/(100-Ht_{baseline})}]-1) \times 100$
 - b. Extracellular fluid (ECF)
 - *i.* Measured by bioimpedance spectroscopy
- 2.2. Relationship between volume and hormones: Volume will be measured by PV and ECF. Hormones will be measured by:
 - a. Hormones activated in HF patients (NT-proANP, BNP)
 - b. Renin-angiotensin-aldosterone system (RAAS) markers (serum aldosterone, renin, PRA, ANGII, AGT, ACE2, ACE)

- c. SNS markers (norepinephrine, epinephrine, heart rate, heart rate variability (SDNN and RMSSD)
- 2.3. Renal hemodynamic function will be measured using the following groups of outcomes:
 - a. Absolute measured values
 - i. mGFR
 - *ii.* ERPF (for site 1 and 2)
 - iii. Hematocrit
 - b. Creatinine-derived values
 - *i.* 24-hour Crt (mmol/day)
 - *ii. Creatinine clearance (ml/min)*
 - c. Gomez-derived values (for site 1 and 2)
 - *i.* RBF = RPF/(1-HCT)
 - *ii.* RVR = MAP/RBF [Mean arterial pressure = MAP]
 - *iii. Filtration fraction* = *GFR/RPF*
 - iv. $PGLO = (GFR/KFG) + 10mmHg + [5 \times (TP/FF \times ln(1/1-FF)-2)]$
 - v. $R_A = [(MAP PGLO)/RBF] \times 1,328$
 - vi. $R_E = [GFR/(KFG \times (RBF-GFR))] \times 1,328$
- 2.4. Blood-pressure lowering effect will be measured using the following group of outcomes:
 - a. blood pressure (systolic [SBP] and diastolic [DBP])
 - b. NICOM parameters
 - c. echocardiographic measures
 - d. systemic vascular resistance
 - e. arterial stiffness
 - *i.* radial, aortic and carotid augmentation index (AIx)
 - *ii.* carotid-radial pulse-wave velocity (PWV)
 - iii. carotid-femoral PWV
- 2.5. SNS activation will be measured by norepinephrine, epinephrine, heart rate and heart rate variability (RMSSD and SDNN).
- 2.6. Changes to urinary natriuretic modulators will be assessed by the level of ACE-2, adenosine, ACE activity, NT-proANP and ANGII, normalized to urine creatinine.
- 2.7. Safety will be assessed by the number of hypoglycemic episodes and serious adverse events.

3. Outcomes for the exploratory objectives:

- 3.1. Volume contraction will be assessed by:

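### The creatinine criterion for acute kidney injury has no baseline reference, so a cumulative rise can escape the category, and the moving reference acts differently by arm from visit to visit

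*Protocol*

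**What the plan says.** Protocol 7.2.3 lists acute kidney injury among the adverse events of interest, with its own eCRF record, and defines it by two routes: "Acute kidney injury is defined as an increase of 40% in serum creatinine from the previous visit or hospitalization due to acute kidney injury".

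Protocol 7.3 uses a different reference for laboratory values in general: "Deterioration as compared to baseline in protocol-mandated laboratory values, or vital signs will be reported as AEs if they fulfil any of the AE criteria". The definition in 7.2.1 is broad enough to include a creatinine rise, since it covers "any unfavourable and unintended sign (for example, an abnormal laboratory finding), symptom, or disease temporally associated with the use of a medicinal product". Neither section gives a numerical threshold for creatinine.

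On sampling, Protocol section 2 says: "Routine biochemistry and safety labs will be drawn at screening, during each physiological assessment and at each the specified office safety visits". Appendix A lists blood creatinine at Visits 1, 3, 4, 5, 6, 8 and 9. Visits 2 and 7 are phone or email contacts without blood samples.

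The protocol expects an early renal effect of the class. Of the tubuloglomerular feedback response, the Introduction says: "These effects are clinically manifested as acute reductions in GFR". Section 11.1 notes that "the transient rise in serum creatinine may reflect a reduction in intra-glomerular pressure". No size is given for either.

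The SAP (Outcomes 2.7) restricts safety: "Safety will be assessed by the number of hypoglycemic episodes and serious adverse events". Analysis 2.7 reports these by arm without a statistical comparison.

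**The concern.** A reference value that moves at every visit can absorb a slow, steady deterioration. No single step is large enough to qualify, although the total change from baseline may be well over 40%. In patients with heart failure on RAAS blockade and often diuretics, that is a pattern a renal safety category would be expected to show.

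The moving reference is also not independent of treatment. If the drug raises creatinine in the first week, the Visit 4 value, which is the reference for Visit 5, tends to be higher in the ertugliflozin arm. The same written rule then corresponds to different changes from baseline in the two arms. With 18 patients per arm, one event is 1/18 = 5.6% of an arm, so the classification of one or two patients changes the descriptive picture.

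**Working it through.** There is no stated figure to reproduce. The check is the arithmetic of the rule.

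**Inputs**
- Threshold: 40% over the previous visit, read as 40% or more (Protocol 7.2.3).
- Previous visit: taken as the previous visit with a creatinine value. Read literally, the visit before Visit 8 is Visit 7, which has none.
- On-treatment steps: Visits 3–4, 4–5, 5–6 and 6–8, so four (Appendix A). Visit 9 follows one week off drug.
- Visit 3 is taken as pre-drug, because "The first dose of blinded study medication should only be administered one day after all randomization visit procedures have been completed". Other sentences in Protocol sections 2 and 6.3 have study medication taken before procedures at Visits 3, 4 and 8. These statements conflict and must be reconciled.
- Early creatinine rise on drug, *e*: **assumed** 5%, 10%, 15% or 20%. The documents give no figure.

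**1. Cumulative rise with no qualifying step**

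After *k* equal steps of size *s*, creatinine is (1 + *s*)^*k* times baseline.
- *s* = 20%, *k* = 4: 1.20^4 = 2.07.
- *s* = 25%, *k* = 4: 1.25^4 = 2.44.
- Limiting case, *s* = 39%: 1.39^2 = 1.93 and 1.39^4 = 3.73.

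Unequal steps behave the same way. The series 100, 125, 150, 180, 215 has steps of 25%, 20%, 20% and 19% and ends 115% above baseline.

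Conversely, the equal step that just reaches 40% over baseline is 1.40^(1/*k*) − 1: 18.3% for two steps, 11.9% for three and 8.8% for four. None of these meets the previous-visit criterion.

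**2. Effect of an early rise on drug**

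- At Visit 4 the reference is the Visit 3 value, so the drug's own rise counts towards the 40%. Further rise needed: 1.40/(1 + *e*) − 1.
- At Visit 5 the reference is the Visit 4 value, which already contains the rise. Bar relative to baseline: 1.40 × (1 + *e*).

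| Assumed *e* | Further rise needed at Visit 4 | Bar at Visit 5, times baseline |
|---|---|---|
| 0 (unchanged placebo patient) | 40% | 1.40 |
| 5% | 33% | 1.47 |
| 10% | 27% | 1.54 |
| 15% | 22% | 1.61 |
| 20% | 17% | 1.68 |

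The two columns move in opposite directions: easier to meet on drug at Visit 4, harder relative to baseline at Visit 5 and for as long as the rise persists.

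**3. Where an unclassified rise would appear**

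- As an ordinary adverse event under Protocol 7.3, if judged to meet the criteria. SAP 2.7 tabulates no non-serious adverse events.
- As acute kidney injury and a serious adverse event, if the patient is admitted for it.
- In the SAP's renal models: creatinine clearance and mGFR under 2.3, blood creatinine under 3.3. These use Visits 3, 4 and 8 only and estimate arm-level effects. Values from Visits 5, 6 and 9 do not enter, and individual patients are not identified.

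**The case against.** The strongest reply is that little is lost. Protocol 7.3 gives large rises from baseline a route into the adverse event record and has mandated laboratory results summarised in the study report. Hospital admissions are serious adverse events, reported by arm. The renal function objective at 1 and 12 weeks is analysed against baseline and placebo. SAP 2.7 matches the protocol's own safety objective. The count of acute kidney injury feeds no test and no stopping criterion. All of this stands, and it limits the point to how an event is classified and displayed.

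A second reply is that a visit-to-visit comparison is defensible for an acute event, and that a Visit 3 reference would count the expected haemodynamic dip towards the event at every visit in the active arm. This also stands. It is a reason to show both counts, not to replace one with the other.

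A reader might infer two stronger things. One is that stepwise rises are never recorded. The documents do not support that, given Protocol 7.3 and the hospitalization route in 7.2.3 itself. The other is that the rule is biased in favour of ertugliflozin. That looks only at Visit 5 onward; at Visit 4 the effect is the reverse. Section 11.1 calls the creatinine rise transient, so how long a raised reference lasts is not known either.

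**Conclusion.** The point holds in a limited form. The creatinine criterion in Protocol 7.2.3 has no baseline reference. A cumulative rise well above 40%, for example to 2.07 times baseline in four steps of 20%, is not classified as the acute kidney injury event of interest unless one step reaches 40% or the patient is hospitalized for it. Sections 7.2.3 and 7.3 measure deterioration from different reference points and must be reconciled.

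The criterion also depends on arm if creatinine rises early on drug, as the protocol expects. The size of that dependence rests on the assumed 5% to 20% and on Visit 3 being pre-drug. Its direction changes between Visit 4 and Visit 5, and the net direction over the trial cannot be determined from the documents.

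The consequence is modest: the primary analysis is untouched and no planned safety comparison depends on this count. It is worth correcting because the correction is cheap.

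**What to change.** Keep the Protocol 7.2.3 definition and its 40% threshold unchanged. In SAP 2.7:

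1. Add a derived flag that compares each post-dose creatinine (Visits 4, 5, 6, 8 and 9) with the Visit 3 value at the same 40%.
2. Report both counts by arm, descriptively and without a test: events under the existing definition and patients with the Visit 3 flag. Show them by visit, since the effect of the early rise differs between Visit 4 and later visits.
3. State which creatinine value serves as the previous visit when the preceding contact has no blood sample (Visit 7 before Visit 8).
4. Add a sentence reconciling the reference points in Protocol 7.2.3 and 7.3.

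The cost is one derived variable from samples already scheduled and one more table. A few more events will be listed, some of them reflecting the expected haemodynamic dip, and a footnote should say so. This is event classification only; it changes no patient care.
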